According to the World Health Organization (WHO), chronic obstructive pulmonary disease (COPD) is the third leading cause of death worldwide, causing 3.23 million deaths in 2019 .[1] The most common root cause of COPD in the United States is cigarette smoke and COPD affects more than 15 million Americans. There are approximately 1.5 million emergency department visits, 700,000 hospitalizations, and 150,000 deaths per year in the United States due to COPD. It is the fourth leading cause of hospital readmission with 20-25% of cases lead to readmission within 30 days of discharge.[2-5] Despite significant decreases in mortality over the last 20 years due to reduction of smoking, it was still the fourth leading cause of death in US in 2019.[4,6] The data on the impact of COPD for 2020 and 2021 is somewhat skewed due to the impact of COVID-19 but for both years it is considered the 6th leading cause of death in the US.[7,8]

A key factor in the high morbidity and mortality of COPD is that it is a progressive and irreversible disease characterized by a limitation of airflow due to a combination of damage to the small airways (bronchiolitis) and parenchyma of the lung (emphysema) due to chronic inflammation. Progression of the disease and the irreversible damage to the lower respiratory tract leads to increasing episodes of acute exacerbations of COPD (AECOPD) during which there is a sustained increase in cough, sputum production, and shortness of breath. AECOPD can be self-limited but can also lead to progressive respiratory failure.

One cause of COPD progression is *Pneumocystis jirovecii* (PJ), a fungal pathogen best known for causing pneumonia in patients with HIV or other forms of immunosuppression. PJ is not typically found in the respiratory tract of healthy adults but is highly prevalent in those with severe COPD, particularly those with AECOPD, and the inflammation caused by PJ has been shown to lead to progression of COPD.

Detection of PJ generally requires a bronchoalveolar lavage (BAL) to sample the lower respiratory tract and then use direct fluorescent antibodies (DFA) to stain the sample for the presence of PJ. In the COPD population, a BAL is often too invasive for their tenuous respiratory status and DFA has very low sensitivity for PJ (~20%).

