
• Carries the diagnosis of COPD and admitted for and admitted with AECOPD to Beaumont, Royal Oak
• AECOPD requires increased cough, increased sputum production, and shortness of breath +/- increased oxygen needs from baseline• Able to produce a sputum sample• Men or women, age ≥40 and <90• Previously enrolled in the EPIC study and PJ detected in their sputum• Currently treated with steroids• Kidney function not severely impaired ($\text{CrCl} \geq 60$)• AST and ALT $\leq 5x$ Upper limit of normal• Willing and able to provide consent to the study	
• Currently diagnosed with pneumonia or COVID• Allergy or hypersensitivity to TMP-SMX• Current ICU admission or mechanical ventilation• Active cancer or chemotherapy (except non-melanoma skin cancer)• Other potentially confounding pulmonary diagnosis• HIV, leukopenia, neutropenia or other immunosuppressive condition or current use of immunosuppressive medications• Presence of gastrointestinal tract abnormalities that would prevent absorption of medications• Patients with concomitant infection requiring antibiotics active against PJ• Concomitant use of coumadin, phenytoin, pioglitazone, repaglinide, rosiglitazone, glipizide or gliburide• Megaloblastic anemia due to folate deficiency• Pregnancy• Expected life span less than 3 months

Table 1: Inclusion/Exclusion Criteria

3 attending physicians, 3 fellows, and 2 residents available to consent. In addition, a nurse coordinator experienced at consenting will be available to consent or assist the physicians with consenting in order to further educate physician trainees who are sub-investigators on this study. Given physician time commitments we expect the nurse may perform a majority of the consenting herself. Patients who consent for participation will be randomized in a 1:1 ratio to one of two groups.

Group #1 – Fifteen patients will receive a suspension with the equivalent of one DS TMP-SMX by mouth every 12 hours.

Group #2 – Fifteen patients will receive a suspension with placebo by mouth every 12 hours.

Randomization will be generated by biostats and sealed envelopes will be held by [name] in the Research Pharmacy to be opened when a patient is recruited. [name] is the only one who will be unblinded and, in case of an emergency, he can break the blind at the request of one of the attending physician investigators.

The Intervention

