The typical treatment of PJ pneumonia is TMP-SMX is 2 DS tablets every 8 hours for 21 days. Higher concentrations of TMP-SMX are needed to treat the cyst form found in PJ pneumonia. For colonized patients who carry the vegetative form of PJ, a standard dose of TMP-SMX is more appropriate and less likely to cause side effects and potential discontinuation. As such the dose to be used for this study is 1 DS Q12H for 10 days. TMP-SMX is a large tablet which is difficult to over-encapsulate for blinding purposes. As such, the Research Pharmacy will supply a TMP-SMX suspension in individual dose syringes or a matching placebo in individual dose syringes for this study. A single syringe for TMP-SMX will contain 160 mg of trimethoprim and 800 mg of sulfamethoxazole, the same amount found in one DS tablet of TMP-SMX. If the patient is discharged prior to completing the 10-day course of the medication, they will be sent home with the remaining days of study medication and a medication diary which ~~IRB NUMBER: 2022-02~~ ~~IRB NUMBER: 2022-02~~ will be collected at the end of therapy visit. Standard operating

procedures used for all clinical trials within the Infectious Diseases Clinical Trials Unit will be followed at discharge including appropriate instruction of the patient on medication use, filling out the medication diary, when to contact the study staff, and making appointments for follow up.

When a patient with PJ pneumonia is hypoxic, the treatment of the PJ in addition to TMP-SMX includes steroids. This is done to minimize the inflammation from the β -D-glucans of PJ that are released when PJ is killed by TMP-SMX. It is unclear if steroids would be needed with the lower expected levels of PJ in the AECOPD patients but, since most patients with AECOPD are treated with steroids in any case, we feel it is safer to only include patients receiving steroids, hence the inclusion requirement of steroid use.

Evaluations

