Upon consent patients will be given the COPD Assessment Test (CAT) (<https://www.mdcalc.com/copd-assessment-test-cat>), a validated scoring system used in COPD patients to assess progression, functional status, and effectiveness of pulmonary rehabilitation.[29–32] Participants will be monitored daily while in the hospital for highest oxygen need, need for non-invasive or invasive mechanical ventilation, and adverse events, daily monitoring will be carried out by the nurse coordinator. Medications used for the treatment of COPD and antibiotics used will be collected retrospectively for each patient. If the patient remains hospitalized at end of therapy, 30 days, or 90 days then follow up will occur in the hospital. Otherwise, the patient will be asked to come to the Infectious Diseases Clinical Research Office for follow up visits at end of therapy (+0-3 days to allow for schedule issues and end of therapy falling on a weekend), 30 days +/- 5 days, and 90 days +/- 10 days. A \$30 stipend will be paid to the participants after each follow up visit. At the end of treatment visit, the medication diary will be collected. At each follow up visit, the nurse coordinator will review the patient's need for oxygen, their medications for the treatment of COPD, any need to see a physician or go to an urgent care or an emergency room for COPD, and any admission to the hospital for COPD. The CAT will be administered at each follow up visit. An expectorated sputum sample will be collected at each follow up visit which will be transported to the Infectious Diseases Research Laboratory for analysis; sputum samples will be processed and analyzed with the Unyvero LRT system for presence of PJ by PCR. The schedule of events for

[figure not shown]

Figure 1: Schedule of Events

the study is shown in figure 1.

Statistical analysis

No formal power analysis was performed, the sample size of 15 patients per arm is felt to be appropriate for a pilot study and appropriate to the funding for this application. We expect to find enough cases of PJ colonization to identify and recruit the 30 patients to be included in the study from the pool of patients for the EPIC study.

Time to return to baseline O2 requirements, and time to next admission for exacerbation will be analyzed using cox proportional hazards regression or other ~~more appropriate time~~ time-to-event analysis method. Need for mechanical

IRB APPROVAL DATE: 06/08/2022

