ventilation will be analyzed using logistic regression. LOS will be analyzed using quantile regression. The number of urgent care/emergency room visits and number of hospitalizations for AECOPD within 3 months and mortality will be analyzed using Poisson regression (or other appropriate method if there is evidence of overdispersion). Durability of decolonization, change in medications for COPD, and CAT score will be a longitudinal analysis. This analysis plan was developed by [name] in Biostatistics who will perform the analysis.

Any participants who withdraw prior to the EOT assessment will be dropped from the study and replaced. Any participants who withdraw after completing the EOT assessment will be analyzed in a modified intent to treat population and not replaced. Only participants who complete all assessments will be analyzed as per protocol.

Anticipated Outcomes

We anticipate treatment of PJ colonized AECOPD patients with standard of care plus TMP-SMX will improve symptoms, decrease LOS and increase the interval free of acute exacerbations above standard of care alone. Using the CAT, we expect to have a quantifiable score which can demonstrate a difference in outcomes between the two groups.

We also anticipate that patients with AECOPD who are colonized with PJ and treated with standard of care alone will maintain colonization over the 3-month period of follow up. Patients who are treated with TMP-SMX in addition to standard of care are expected to have microbiological eradication of PJ colonization and we expect that eradication to last through the 3-month follow up visit.

Potential problem areas and alternative tactics

This study is relatively simple and straight forward, we do not anticipate any issues with identifying or recruiting patients for the study but recognize that recruitment can be lower than expected for any study.

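### Randomised participants who withdraw before the end-of-therapy assessment are removed and replaced, so the comparison of arms is conditional on a post-randomisation event

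*Combined protocol and SAP*

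**What the plan says.** The Patients section of the combined protocol and SAP places allocation soon after consent: "Patients who consent for participation will be randomized in a 1:1 ratio to one of two groups". The Intervention (under Study design) gives a 10-day course, and Evaluations puts the end-of-therapy (EOT) visit 0 to 3 days after it.

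The Statistical analysis section then has three rules:

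- Before EOT: "Any participants who withdraw prior to the EOT assessment will be dropped from the study and replaced".
- After EOT: "Any participants who withdraw after completing the EOT assessment will be analyzed in a modified intent to treat population and not replaced".
- Completers: "Only participants who complete all assessments will be analyzed as per protocol".

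Outcome data start to accrue well before EOT. Evaluations says: "Participants will be monitored daily while in the hospital for highest oxygen need, need for non-invasive or invasive mechanical ventilation, and adverse events". No all-randomised set, safety set, missing-data method or sensitivity analysis is described. How replacements are allocated is not stated either.

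**The concern.** Randomisation makes the two arms comparable at allocation. If people are removed afterwards for a reason that may depend on treatment and on prognosis, the groups left need no longer be comparable. Here the condition for being analysed is staying in the study for about 10 to 13 days. Tolerability, lack of improvement or early recovery could all influence that, and blinding does not prevent any of them. Calling the remaining set modified intent to treat does not restore comparability.

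The rule also wastes data. Ventilation in the index admission, length of stay and return to baseline oxygen can all be known before EOT. A patient discharged on day 4 who withdraws on day 7 could have all three recorded and still be dropped.

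The plan does not separate *withdraw* from stopping study drug or from death. Mortality is an analysed outcome, so early deaths and early adverse events could be lost on one reading, although the text does not say so.

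The results are meant to inform a larger trial, which needs retention and tolerability figures for everyone randomised. With 15 per arm, or 10 under the fallback in Potential problem areas and alternative tactics, a few removals are a sizeable share.

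**Working it through.** The plan gives no power, effect size or withdrawal rate, so there is no figure of its own to reproduce. The finding rests on step 1; the later steps show scale under stated assumptions.

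**1. Who is in which set**

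| Status after randomisation | Modified ITT | Per protocol |
|---|---|---|
| Withdraws before EOT | no (dropped, replaced) | no |
| Withdraws after EOT | yes | no |
| Completes all assessments | presumably (not written) | yes |

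Everyone analysed has reached EOT.

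**2. Shift in a risk difference when there is no true effect**

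Let p be the event risk, and let we and wn be the probabilities of early withdrawal with and without the event. The risk seen among those who reach EOT is

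p(1−we) / [p(1−we) + (1−p)(1−wn)].

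The only event figure in the documents is in Specific Aims, for COPD generally: "20-25% of cases lead to readmission within 30 days of discharge". I use p = 0.20 and 0.25 from it, with 0.10 and 0.30 as a range. Withdrawal rates are assumed: wn = 0.10 throughout, and we = 0.20 or 0.40 in the TMP-SMX arm with 0.10 in the placebo arm. The reverse case has we = 0.30 in the placebo arm and 0.10 in the TMP-SMX arm. Differences are TMP-SMX minus placebo, in percentage points.

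| p | TMP-SMX we = 0.20 | TMP-SMX we = 0.40 | Reverse: placebo we = 0.30 | SE, 15 per arm |
|---|---|---|---|---|
| 0.10 | 0.08/0.89 = 0.090; −1.0 | 0.06/0.87 = 0.069; −3.1 | 0.07/0.88 = 0.0795; +2.0 | 11.0 |
| 0.20 | 0.16/0.88 = 0.182; −1.8 | 0.12/0.84 = 0.143; −5.7 | 0.14/0.86 = 0.163; +3.7 | 14.6 |
| 0.25 | 0.200/0.875 = 0.229; −2.1 | 0.150/0.825 = 0.182; −6.8 | 0.175/0.850 = 0.206; +4.4 | 15.8 |
| 0.30 | 0.24/0.87 = 0.276; −2.4 | 0.18/0.81 = 0.222; −7.8 | 0.21/0.84 = 0.250; +5.0 | 16.7 |

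The standard error is √[2p(1−p)/15]. The largest ratio of shift to standard error is at p = 0.30: 0.078/0.167, or just under one half.

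**3. A second set of assumptions**

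Take p = 0.30, overall early withdrawal of 20% (TMP-SMX) v 5% (placebo), and patients with the event 2 to 3 times as likely to withdraw in both arms. The shift is −3.2 to −5.2 points. At 30% v 5% it is −6.1 to −9.9, the last being about 0.6 of the standard error (9.9/16.7).

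**4. When the shift vanishes**

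It is zero if withdrawal is unrelated to outcome or, with no true effect, if the relation is the same in both arms. With a true effect, an equal relation still distorts. With we = 0.30 and wn = 0.10 in both arms and true risks of 20% v 40%, the plan would see 0.14/0.86 = 16.3% v 0.28/0.82 = 34.1%. That is −17.9 points against a true −20.0.

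**5. How many are removed**

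With early withdrawal d and replacement up to n per arm, n/(1−d) are randomised per arm.

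| n per arm | d | Randomised per arm | Total, rounded up per arm | Removed | Removed, unrounded: 2nd/(1−d) |
|---|---|---|---|---|---|
| 15 | 10% | 16.7 | 34 | 4 | 3.3 |
| 15 | 20% | 18.75 | 38 | 8 | 7.5 |
| 10 | 10% | 11.1 | 24 | 4 | 2.2 |
| 10 | 20% | 12.5 | 26 | 6 | 5.0 |

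**The case against.** The reading of the analysis sets is not seriously open to dispute, but its importance can be questioned.

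- **No evidence of differential withdrawal.** The Intervention describes the chosen dose as "less likely to cause side effects and potential discontinuation" in comparison with the higher pneumonia dose, and discontinuation there most naturally means stopping drug. This stands as a limit: the passage shows that the authors see tolerability as a possible cause of stopping, not that withdrawal will differ by arm. Placebo and blinding remove some causes of differential withdrawal, but not side effects or lack of improvement.
- **Little opportunity to withdraw.** The window is short, visits carry a stipend, and "If the patient remains hospitalized at end of therapy, 30 days, or 90 days then follow up will occur in the hospital". These may keep numbers low but do not exclude bias.
- **Dropped might mean only that follow-up stops.** This is possible, but the next sentence says that later withdrawers, by contrast, will be analysed. The text favours exclusion and nothing elsewhere reverses it.
- **The illustration uses readmission.** Most readmissions would follow an early withdrawal, so the calculation presumes a link between leaving early and a later event. The plan also counts admissions over 3 months, not 30 days. This is fair: the figures show scale only, and no separate estimate is available for oxygen or ventilation.
- **Best/worst-case bounds will be wide.** With 2 of 17 missing per arm they span 2 × 2/17 = 23.5 points; with 4 of 19, 2 × 4/19 = 42.1. That is true, and it is why they serve as a sensitivity analysis only.
- **It is a pilot.** The plan admits it may not detect differences. It still compares arms by regression and intends to build on the results.

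**Conclusion.** The concern holds. As written, the plan removes randomised participants on a post-randomisation event and gives them no place in any analysis set. That follows from the text and needs no assumption.

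The size does depend on assumptions, because the documents give no withdrawal rates and fix no direction. The main scenarios give shifts of 1 to 8 points in either direction, all under half a standard error. The more extreme set reaches about 10 points, or 0.6 of a standard error. Reporting withdrawals by arm would reveal differential loss but would not correct the estimate. The issue is validity and avoidable loss of data; nothing here suggests that a result would be reversed.

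**What to change.** Replace the sentence on early withdrawal with wording such as:

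> All randomised participants are analysed in their assigned arm, using all data collected up to withdrawal and, where consent allows, later outcomes from medical records. Withdrawal from the study is distinguished from stopping study drug, after which follow-up continues, and from death, which is counted as an outcome. Additional participants may be randomised, but no randomised participant is removed.

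Also:

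- State who belongs to each analysis set and how additional participants are allocated.
- Report adverse events for everyone who took study drug, and withdrawals by arm and reason.
- Keep the analysis of those who reach EOT as secondary.
- Because censoring at withdrawal may be informative, add one best/worst-case sensitivity analysis for missing outcomes. For return to baseline oxygen and next admission, contrast an event at withdrawal with event-free to the end of follow-up. For ventilation and PCR clearance, impute each of the two possible values. A shift model for the CAT score is optional.

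The cost is protocol and SAP wording plus one small analysis. The change cannot recover CAT or PCR results for early withdrawers, since both are first collected after baseline at EOT. Use of records after withdrawal depends on consent wording not seen here. The number randomised may exceed 30, as it already would under replacement.

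### The per-protocol set is defined by completing follow-up to day 90, not by treatment received, so it excludes fully treated patients who die or withdraw after end of therapy

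*Combined protocol and SAP*

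**What the plan says.** The Statistical analysis section has three sentences on who is analysed. On early leavers: "Any participants who withdraw prior to the EOT assessment will be dropped from the study and replaced". On later leavers: "Any participants who withdraw after completing the EOT assessment will be analyzed in a modified intent to treat population and not replaced". On the per-protocol set: "Only participants who complete all assessments will be analyzed as per protocol". No other condition for that set appears in the visible text. No set is called primary, and outcomes are not assigned to sets. Mortality is among the outcomes to be modelled.

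The study-design section headed The Intervention sets the planned course at one dose every 12 hours for 10 days, with a medication diary for patients discharged before finishing. Under Evaluations, follow-up visits fall at EOT (up to 3 days late) and then at "30 days +/- 5 days, and 90 days +/- 10 days". At these visits "The CAT will be administered at each follow up visit" and "An expectorated sputum sample will be collected at each follow up visit". The diary comes in at the first of them: "At the end of treatment visit, the medication diary will be collected".

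**The concern.** A per-protocol analysis is normally read as describing patients treated as planned. Here the stated condition is about attendance, and it stays open for more than two months after the last dose. Someone who followed the treatment plan exactly can still be removed by a later event, including death, that may itself be an outcome of the disease or the treatment. The resulting set describes survivors who finished follow-up.

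The pilot is meant to inform larger trials. A per-protocol column with no deaths before the final visit, and without the patients who left after EOT, could be misread as the effect of treatment taken as directed.

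**Working it through.** The plan gives no figure to reproduce: the sample size of 15 per arm comes without a power calculation, and no adherence, death or withdrawal rate is stated. The check applies the rule as written.

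**Planned exposure.** 10 days x 2 doses per day = 20 doses. The per-protocol sentence states no minimum number.

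**How long membership stays open after EOT.** The visible text does not say whether visit days count from the first dose or from end of therapy, and the schedule figure is not shown, so both are given.
- From first dose: EOT visit at day 10 to 10 + 3 = 13; final visit at day 90 - 10 = 80 to 90 + 10 = 100. Gap: 80 - 13 = 67 days to 100 - 10 = 90 days.
- From end of therapy: EOT visit at day 0 to 3; final visit at day 80 to 100. Gap: 80 - 3 = 77 days to 100 - 0 = 100 days.

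**The rule applied to five patients.**

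| Patient | Completes all assessments? | Modified intent-to-treat set |
|---|---|---|
| All 20 doses, every visit | Yes | In, by implication |
| All 20 doses, withdraws after EOT | No: excluded from per protocol | In, as stated |
| All 20 doses, dies after EOT and before the final visit | No: excluded from per protocol | Death not named; nothing removes the patient |
| Few doses, every visit | Yes; no stated rule excludes them | In, by implication |
| Withdraws before EOT | No; dropped and replaced | Not in |

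**Data left out of the per-protocol analysis.** There are 3 follow-up sputum samples (EOT, day 30, day 90) and 4 COPD Assessment Test scores (consent plus 3 visits). A patient lost after EOT has given 1 of 3 and 2 of 4. A patient lost after day 30 has given 2 of 3 and 3 of 4. None of these enters the set.

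**Mortality.** A patient who dies before the final visit cannot complete it, so per-protocol deaths before that visit are 0 in each arm whatever the true rate. Illustration only, on assumed 90-day mortality of 5%, 10% or 20%: expected deaths in an arm of 15 are 15 x 0.05 = 0.75, 15 x 0.10 = 1.5 or 15 x 0.20 = 3.0. The per-protocol count is 0 in every case.

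**Weight of one patient.** 1/15 = 6.7% of a planned arm, or 1/10 = 10% of the fallback arm in Potential problem areas and alternative tactics.

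**The case against.** The strongest reply is that the word only gives a necessary condition. The sentence does not say that everyone who completes all assessments is per protocol, and an adherence condition could exist elsewhere. The schedule figure is not shown, so a dose or diary review may be among the listed assessments. Stopping study drug might also be treated as withdrawal. This stands. A reader might infer that the plan deliberately keeps patients who took few doses; the documents support only that no visible sentence excludes them. The reply does not touch the other half of the point: a necessary condition is enough to exclude fully treated patients who die or leave.

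Second, the effect is limited. Withdrawals after EOT are expressly kept in the modified intent-to-treat set. Table 1 excludes patients in intensive care, on ventilation or expected to live less than 3 months, which should keep deaths few. The trial is an unpowered pilot. All this stands and limits the weight of the point, but it does not repair the per-protocol set.

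Third, a reader might infer more than the documents bear:
- That the plan expects patients to stop treatment. The dose rationale mentions discontinuation only to argue that the chosen dose makes it less likely.
- That missed doses could never be told apart from the plan's own explanations for clinical improvement without eradication. The diary and inpatient records would allow at least a listing by patient.
- That poorly adherent patients would shrink every estimate by their share of the arm. That arithmetic fits a difference in means or proportions with no effect in those patients. It does not carry over to the planned Cox, logistic, Poisson and quantile models.

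Finally, a dose-based set also selects on behaviour after randomisation. That is true, and it is why the set should be supportive only.

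**Conclusion.** The point holds in a limited form. The stated rule makes the per-protocol set a completers set: it selects on survival and attendance for 67 to 100 days after the EOT visit, depending on the day count and visit windows. Deaths before the final visit are zero in it by construction. It also lacks a visible adherence criterion, which is an omission and not an explicit decision to keep poorly dosed patients.

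The damage is confined to per-protocol results. The number of patients affected cannot be estimated from the documents, and the mortality rates used above are assumptions; the conclusion does not depend on them. It does assume that the schedule figure adds no dose criterion and does not change what completing all assessments means. This is a worthwhile, inexpensive correction to a supportive analysis, not a threat to the trial's main comparison.

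**What to change.** Before unblinding, replace the per-protocol sentence with a definition based on treatment received:

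- Membership: met the eligibility criteria and took at least a stated share of the 20 planned doses. The investigators choose the share.
- Source: inpatient administration records (assumed to be kept as routine hospital records; the plan does not mention them) and the existing home diary. The diary is collected at EOT, so for patients who leave later the adherence data should already be in hand.
- Follow-up: do not require survival or attendance to day 90. Use each member's data up to death or withdrawal.
- Labelling: call any analysis restricted to patients with all assessments a completers analysis, and say whether a visit without a sputum sample counts as complete.
- Reporting: show the modified intent-to-treat result beside the per-protocol result.

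The rule on withdrawals before EOT is a separate matter and is left as it stands here.

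The cost is analysis wording and a dose count per patient; no visit or test is added. There are two downsides. Home adherence is self-reported, and a dose-based set still selects on events after randomisation, so it should be presented as supportive only.
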